### **1. Abstract** (*provide no more than a one-page research abstract briefly stating the problem, the research hypothesis, and the importance of the research.*)

We hope to gain an understanding of the utility of pure cannabidiol (CBD) used for the treatment of medically refractory epilepsy in Sturge-Weber syndrome (SWS) in this open-label, safety dose-finding, study. Children living with medically refractory epilepsy urgently need more effective medications. Among children with medically refractory epilepsy, those suffering from early-onset and high seizure burden epilepsies suffer the greatest neurodevelopmental problems, including intellectual disability and autism. SWS typically presents in the first year of life with seizures in children with otherwise fairly normal development. About 50% of cases involving medically refractory seizures either at seizure onset, or loss of seizure control, will occur in childhood. Prolonged and repeated seizures in patients with SWS are frequently associated with new neurologic deficits, loss of developmental milestones, and either neurologic regression or slowing in cognitive development. In addition, seizure activity in SWS patients often leads to the development of brain atrophy, hemiparesis, cognitive impairment, and vision deficits. Recent evidence suggests that CBD has multiple, beneficial, effects in patients (such as those with SWS that undergo neurological deterioration) suffering from medically refractory seizures. We hypothesize that CBD will reduce seizure frequency in children and young adults with SWS and will therefore help stabilize and improve their neurologic status. This trial is part of an expanded access program, available through a partnership with GW Pharmaceutical, which has been sanctioned by the FDA to study the safety and efficacy of Epidiolex (cannabidiol/CBD) in participants with SWS and medically refractory seizures.

### **2. Objectives** (*include all primary and secondary objectives*)

The primary objective of this study is to determine the tolerability and optimal dose of CBD as an adjunct treatment in children and young adults with Sturge-Weber syndrome and drug resistant epilepsy.

Beneficial effects of CBD-enriched cannabis other than reduced seizures included better mood (15/19, 79%), increased alertness (14/19, 74%), better sleep (13/19, 68%) and decreased self-stimulation (6/19, 32%). Negative side effects included drowsiness (7/19, 37%) and fatigue (3/19, 16%). Limitations of this data include lack of control data, lack of randomization, and no blinding associated with open-label use, as well as uncertainty of the dosage in artisanal preparations. However, this survey does lend hope that CBD may be a useful pharmaceutical alternative to existing therapies in drug resistant epilepsy, and sheds light as to what doses are being used experimentally that seem to be tolerated. Our study will extend these previous studies to those with Sturge-Weber syndrome and medically refractory epilepsy and will directly study in a clinical research setting both the benefits and the side effects of a pharmaceutical grade preparation of CBD.

#### 4. Study Procedures

a. *Study design, including the sequence and timing of study procedures (distinguish research procedures from those that are part of routine care).*

**Study Overview:** Investigator Initiated Expanded Access Study in 10 participants with Sturge-Weber syndrome brain involvement, medically refractory seizures and [name] participants at the Hunter Nelson Sturge-Weber Center at the Kennedy Krieger Institute

We hope to gain an understanding of the utility of pure CBD use for the treatment of drug resistant epilepsy in Sturge-Weber syndrome in this open-label dose-finding observational study. A baseline seizure frequency will be recorded for each subject in a diary for eight weeks prior to investigational drug initiation and parents/caregivers will document seizures on a daily basis throughout the study period (see seizure log). Investigational drug (CBD) will be administered as an adjunct to all current anti-epileptic drugs. All subjects will, at minimum, be clinically evaluated at screening, baseline, weekly for the first 6 weeks after drug initiation, then 4 weeks and 8 weeks later during the Core Phase. During the Optimization Phase they will be followed every 6-12 weeks (see Study Visits Table for precise timeline).

PROPRIETARY MATERIALS OF THE HUGO W. MOSER RESEARCH INSTITUTE AT KENNEDY KRIEGER, INC. DO NOT USE OR DISCLOSE WITHOUT PERMISSION OF THE RESEARCH INSTITUTE

**Method of administration:** Cannabidiol oral solution 100 mg/ml will be administered orally. The participants will be treated on an outpatient basis and will not require inpatient hospital admission.

**Dose / titration schedule:** Initiation of treatment will begin with 2 mg/kg/day given in two divided doses. The dose will be increased by 3 mg/kg/day after seven days and then by 5 mg/kg/day every seven days up to a maximum dose of 25 mg/kg/day given. The dosing schedule will be as follows, as tolerated:

- Start of study : 2 mg/kg/day; subject will be evaluated here
- Week 1: Increase dose by 3 mg/kg/day for total daily dose of 5 mg/kg/day; subject will be evaluated here
- Week 2: Increase dose by 5 mg/kg/day for total daily dose of 10 mg/kg/day; subject will be evaluated here
- Week 3: Increase dose by 5 mg/kg/day for total daily dose of 15 mg/kg/day; subject will be evaluated here
- Week 4: Increase dose by 5 mg/kg/day for total daily dose of 20 mg/kg/day; subject will be evaluated here
- Week 5: Increase dose by 5 mg/kg/day for total daily dose of 25 mg/kg/day; subject will be evaluated here

If a subject responds well to an intermediate dose during the Core Phase, he or she may be maintained at that dose and does not need to complete escalation. Escalation may resume during the Optimization or Extension Phase if there is a temporary increase in seizures. If escalation resumes, the dose will be increased by 5mg/kg/day at each visit up to a maximum of 25mg/kg/day.

The dose of concomitant anti-epileptic drugs will remain unchanged during the first 14 weeks of CBD treatment (or until 8 weeks after steady state at final dose), unless symptoms of toxicity and/or significant changes in blood levels are observed.

#### **Measurement of changes in seizures (Routine)**

Change in seizure frequency is the primary outcome measure for this pilot trial. All seizure types will be classified before study entry. Seizure frequency for each seizure type will be recorded during a baseline of 8 weeks before administration of CBD. Seizure type, frequency will be monitored during baseline and treatment as recorded in a patient diary (see seizure log). For assessing the efficacy of CBD, the investigator will count the change in the frequency of seizures (i.e., tonic seizures, clonic seizures, tonic-clonic seizures lasting more than 3 seconds, focal motor seizures, focal seizures with impaired consciousness, atonic seizures, myoclonic seizures including myoclonic absences). In addition, parents/caregivers will report the following **secondary outcome measures**:

- Change in average seizure duration by seizure type
- Change in the number of episodes of status epilepticus, defined as convulsive seizure lasting longer than 10 minutes
- Change in the number of uses of rescue medication
- Change in the number of ER visits/ hospitalizations

### Laboratory tests and clinical procedures

- Weight, vitals and orthostatics will be monitored at baseline and at each visit. For subjects who are physically unable to complete standing orthostatics, only supine orthostatics will be collected. (Routine care)
- Neuroscores will be assigned at each visit by [name] as per her clinical routine. Neurologic exam and general physical exam will also be performed at each visit. (Routine care)
- Participants will be asked at each clinic visit about migraine frequency, severity (scale of 1-10) and duration, and any change in neurologic symptoms
- CBC, LFT, BUN, creatinine levels, electrolytes, will be measured at baseline, one month after baseline, one month and two months after maintenance dose steady state is reached, every 2-3 months during the Optimization Phase, and every three months (at each visit) during extension phase. Urine analysis will be performed at each of the extension phase visits (every three months).
- For subjects with a facial port-wine birthmark, frontal and profile photograph will be taken under standardized conditions with scoring of the port-wine birthmark for percent of face covered, thickness of birthmark, and darkness of birthmark color. Subjects without any facial port-wine birthmark will only need photographs taken at a single visit to confirm the lack of birthmark. (Research, See Study Visit Table)
- Concomitant AED plasma concentrations will be measured at baseline, one month after baseline, at steady state maintenance CBD dose, one month and two months after maintenance dose steady state is reached, every 2-3 months during the Optimization Phase, and at each extension phase visit.
- CBD plasma concentrations will be measured twice, at 6 and 10 weeks after baseline.
- hCG urine pregnancy test will be used for all female participants Tanner stage 2 and above (see Study Visit Table). We will tell subjects that they must be using effective birth control (for example, abstinence, birth control pills, contraceptive implants, condoms) and confirm that this is the case at each study visit. We will inform female subjects that they should not become pregnant or breastfeed a baby while on this study or for 30 days after taking Cannabidiol. We will also inform male subjects that they should not get their partners pregnant while on this study or for 30 days after taking Cannabidiol. Anyone who becomes pregnant while on the study will be removed immediately.
- Forms generated for use as case report forms will also be used as source documents. Forms will be filled out during the study visit with data. *Immediately* after the visit, the form will be photocopied and one copy will *immediately* have the study subject ID# written on it (case report form). The other copy will *immediately* have the subject name written on it (source document).

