#### b. Study duration and number of study visits required of research participants.

1. **Duration of therapy:** Once optimal dose is found (25 mg/kg/day or maximal tolerated dose; expected to be reached within 5 weeks), participants may continue on the **Core Phase** for a minimum of 8 weeks after reaching steady state; during this time the dose of their other anticonvulsants will not be changed unless signs of toxicity or significant changes in blood levels are observed. This will be followed by 28 weeks of an **Optimization Phase** during which the subject will be followed every 6-12 weeks (see Study Visits for details) and doses of other anticonvulsants may be changed to optimize seizure control. After the Optimization Phase, subjects will be offered the opportunity to enter the **Extension phase** and continue on CBD with clinical follow-up every 3 months. Optimal dosing is proposed by GW Pharm Inc, based upon their preclinical studies and clinical experience to date.

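### A subject escalating on schedule has no scheduled liver panel between about week 4 and week 10, although the steps to 20 and 25 mg/kg/day fall at weeks 4 and 5 and blood is drawn at week 6

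*Combined protocol and SAP*

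**What the plan says.** **Scheduled liver tests.** Section 4a, Laboratory tests and clinical procedures, reads: "CBC, LFT, BUN, creatinine levels, electrolytes, will be measured at baseline, one month after baseline, one month and two months after maintenance dose" steady state, and then at longer intervals in the Optimization and Extension Phases. The list of anti-epileptic drug (AED) levels in the same section includes a draw at steady state itself. The liver-test list does not.

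**Dose steps.** Section 4a, Dose / titration schedule, has "Week 4: Increase dose by 5 mg/kg/day for total daily dose of 20 mg/kg/day" and "Week 5: Increase dose by 5 mg/kg/day for total daily dose of 25 mg/kg/day". Section 4b says the optimal dose is "expected to be reached within 5 weeks".

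**Visits and other blood draws.** Section 4a places visits "weekly for the first 6 weeks after drug initiation, then 4 weeks and 8 weeks later during the Core Phase". It adds: "Neurologic exam and general physical exam will also be performed at each visit". On drug levels: "CBD plasma concentrations will be measured twice, at 6 and 10 weeks after baseline".

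**Unscheduled liver panels.** Section 4b, Study Visits, requires a repeat within 72 hours when ALT or AST exceeds 3 times the upper limit of normal (ULN). It also requires a panel after a study-drug dose increase that follows the escalation phase, after a change to another liver-active drug, or for listed symptoms with no other explanation.

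**Stopping rules.** Section 4f, item 8, stops treatment on defined ALT/AST results: for example above 8 times ULN, or above 5 times ULN lasting more than 2 weeks.

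**The concern.** The 72-hour repeat and the ALT/AST stopping rules can act only on a result that has been obtained. If the liver-test list is the whole schedule, a symptom-free rise that follows the step to 20 or 25 mg/kg/day produces no scheduled result until week 10.

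The plan already treats a dose increase as a reason to test the liver, but only after the escalation phase. For a subject held at an intermediate dose, Section 4a says: "If escalation resumes, the dose will be increased by 5mg/kg/day at each visit up to a maximum of 25mg/kg/day". A subject held at 15 mg/kg/day who later steps to 20 or 25 must therefore have a panel. A subject who makes the same steps at weeks 4 and 5, on first exposure to those doses, need not.

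Tolerability and the optimal dose are the primary objective (Section 2). Section 8b describes safety data on pure CBD as limited (item 4) and the effects with AEDs metabolized by the inhibited enzymes as unknown (item 6).

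**Working it through.** The plan states no liver-test interval, so the calendar has to be built from its parts.

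**Inputs**
- Visit spacing: Section 4a, Study Overview. Visit 2 is baseline and Visit 10 ends the Core Phase (Section 4b, Study Visits).
- Dose steps: Section 4a. 15 mg/kg/day from week 3, 20 from week 4, 25 from week 5.
- Steady state: Sections 4a and 4f equate 14 weeks on drug with 8 weeks after steady state.
- Assumption: 1 month = 4 weeks.

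**Step 1: visits.** Visit 2 = week 0; Visits 3 to 8 = weeks 1 to 6; Visit 9 = 6 + 4 = week 10; Visit 10 = 6 + 8 = week 14. Check: CBD levels are at weeks 6 and 10 in Section 4a and at Visits 8 and 9 in Section 8b, item 6. The two agree.

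**Step 2: steady state.** 14 − 8 = week 6.

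**Step 3: scheduled liver tests.** Baseline = 0; one month after baseline = 4; one month after steady state = 6 + 4 = 10; two months after = 6 + 8 = 14.

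**Step 4: dose behind each sample.** The step to 20 is made at the week-4 visit, so a sample there follows a week at 15. The first scheduled panel at 20 or more is at week 10.

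**Step 5: intervals, current list against an added week-6 panel**

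| Quantity | Current list | With week-6 panel |
|---|---|---|
| Step to 20 → first panel | 10 − 4 = 6 weeks | 6 − 4 = 2 weeks |
| Step to 25 → first panel | 10 − 5 = 5 weeks | 6 − 5 = 1 week |
| Share of Core Phase time at 20 or more before that panel (14 − 4 = 10 weeks) | 6/10 = 60% | 2/10 = 20% |
| Share of Core Phase time at 25 before that panel (14 − 5 = 9 weeks) | 5/9 = 56% | 1/9 = 11% |
| Longest gap between Core Phase panels | 10 − 4 = 6 weeks | 4 weeks |

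**Step 6: effect on a stopping rule.** Take a symptom-free rise above 5 times ULN already present at week 6, and count duration from the first documented result. Under the current list, the rule that needs more than 2 weeks can be met only after 10 + 2 = week 12, which is 12 − 5 = 7 weeks after the step to 25. With a week-6 panel it can be met after 6 + 2 = week 8, which is 8 − 5 = 3 weeks after. The difference is 4 weeks.

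**Sensitivity**
- Steady state at week 5: the panel falls at 5 + 4 = week 9, which is 9 − 4 = 5 and 9 − 5 = 4 weeks after the two steps. No visit is planned at week 9.
- Month of 4.29 weeks (30 days) or 4.35 weeks (calendar), steady state at week 6: 6.29 to 6.35 and 5.29 to 5.35 weeks.
- A literal 30-day month would put the second panel 30 − 28 = 2 days after the step to 20. The weekly visits point to week 4 instead, as does the AED draw at Visit 6 (Section 8b, item 6). Two days at 20 would in any case say little.

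**The case against.** **The Visit Table may settle it.** Several sections defer to a Visit Table that is not in the text available for review. If it lists a week-6 panel, only the wording of Section 4a is incomplete. This stands as a limit. The one visit-numbered list of safety draws in the text, for AED levels in Section 8b, item 6, gives Visits 2, 6, 9 and 10 in the Core Phase, which are weeks 0, 4, 10 and 14. That matches the calendar above. It is not direct evidence, because it concerns AED levels and itself omits the steady-state AED draw listed in Section 4a.

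**The different treatment of later dose increases may be deliberate.** Planned escalation has weekly visits with an exam, whereas resumed escalation happens when visits are 6 to 12 weeks or 3 months apart. That is a coherent reason for an extra panel later. It does not make an exam a substitute for a blood result, and visits stop being weekly after week 6.

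**Other cover exists.** Section 8b asks for evaluation at least monthly above 600 mg per day until steady state (item 2) and close monitoring for side effects during titration (item 5). The symptom trigger in Section 4b is broad. All of this is true, but neither Section 8b item names a liver test. Symptoms are also a weaker signal in subjects who may be 1 month old (Section 5), and fatigue is already a listed side effect of the drug (Section 8a). What remains uncovered is a rise with no recognized symptom and no change in another liver-active drug.

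**The benefit is unquantified.** This stands. The percentages restate calendar gaps and are not risks. Week 6 is only one week after the step to 25, and a rise that starts after week 6 would still first be seen at week 10.

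**The 2-week rule is a selective example.** The other criteria carry no such wait. The gain is still 4 weeks for them, because the first scheduled result moves from week 10 to week 6.

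**Conclusion.** The concern holds. Under the Section 4a list, a subject who escalates on schedule has no scheduled liver test from about week 4 to week 10. The first one at 20 mg/kg/day or more comes 6 weeks after the step to 20 and 5 weeks after the step to 25, or 5 and 4 weeks if steady state is taken as week 5. For a symptom-free rise already present at week 6, the repeat-test and stopping rules could act up to 4 weeks earlier with one added panel.

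This rests on 4-week months, on-schedule escalation, and a Visit Table that adds no week-6 panel. Subjects kept at 15 mg/kg/day or less are not affected. The documents give neither the frequency nor the onset time of ALT/AST rises, so the number of events caught cannot be stated. The point concerns safety monitoring and does not touch the efficacy endpoint. It is a change the sponsor should make because it is cheap and follows the plan's own practice after escalation; confidence is medium because the Visit Table could not be checked.

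**What to change.** Check the Visit Table first. If it already lists a week-6 liver panel, align Section 4a with it. If not, amend both so that ALT/AST, total bilirubin and alkaline phosphatase are run on the Visit 8 (week 6) blood already drawn for CBD levels. Panels then fall at weeks 0, 4, 6, 10 and 14.

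Optional: for subjects who reach their maintenance dose after week 5, run the same panel on the steady-state AED sample in Section 4a, where that sample is actually taken.

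The cost is one extra assay in about 10 subjects and a small added blood volume, which matters most in infants. No new visit or venipuncture is needed, and the optional panel adds no draw. Weeks 6 to 10 would still have no scheduled panel.

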### *c. Blinding, including justification for blinding or not blinding the trial, if applicable.*

During this pilot expanded access study, where the primary objectives are to assess tolerability and dose, blinding is not appropriate. There is no placebo or non-treatment group that would require blinding.

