### *b. Secondary outcome variables.*

Neurologic score

Port-wine score

Frequency and severity of side effects

Seizure duration

Number of episodes of status epilepticus, defined as convulsive seizure lasting longer than 10 minutes

Number of uses of rescue medication

Number of ER visits/ hospitalizations

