6. CBD is an inhibitor of CYP 2C19, CYP 2C9, and other cytochrome P450s belonging to the 2C and 3A subfamilies. The effects of CBD administered concomitantly with anti-epileptic drugs that are metabolized by this enzyme system are unknown. Plasma levels of CBD and its metabolites will be measured at study visits 8 and 9 (see Visit Table). Concomitant anti-epileptic drug plasma levels will be measured at baseline, at study visits 2, 6, 9, 10, 12, 13, and at all extension phase visits if participating (see Visit Table). Anti-epileptic drug doses will be adjusted as needed based on signs and symptoms of toxicity and / or changes in drug levels (routine care).
7. We realize that participation in this study is a significant time commitment; therefore we will do our best to schedule at their convenience.

*c. Plan for reporting unanticipated problems or study deviations.*

All adverse events, unanticipated problems, protocol deviations or other concerns will be promptly reported to the principal or co-investigator who will have primary responsibility for notifying the IRB and the KKI Office of Research Compliance. As stated previously, no serious risks are anticipated. All side effects or adverse events problems of a medical nature will also be reported to GW Pharmaceutical.

Study deviations will be reported to the Johns Hopkins IRB as below. Study deviations which impact the interpretation of the data with regards to drug safety of efficacy also will be reported to GW Pharmaceuticals.

*d. Legal risks such as the risks that would be associated with breach of confidentiality.*

The legal risks are minimal as all proper steps will be taken to maintain subject confidentiality and to make the subject feel comfortable and aware of any risks. Photographs will be stored in a digital, locked research database. Participants will have the option to select on the consent form between having these photographs destroyed at the end of the study once all data has been analyzed and published, or allowing the photographs to be relocated to our general data collection photographic database.

*e. Financial risks to the participants.*

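### No masking of visit order is specified for scoring the port-wine photographs; reading coded images in random order would reduce expectation bias at little cost

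*Combined protocol and SAP*

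**What the plan says.** - Section 4a, Laboratory tests and clinical procedures: for subjects with a facial birthmark, a "frontal and profile photograph will be taken under standardized conditions with scoring of the port-wine birthmark". Three components are scored: the share of the face involved, thickness and darkness. The item is marked as research, not routine care. Subjects without a facial birthmark are photographed at one visit only, to confirm its absence.
- The same list names a scorer for the neuroscores but none for the birthmark. It refers to a Study Visit Table, which is not in the text available for this review.
- The last item in that list sets a general rule for case report forms: "Forms will be filled out during the study visit with data".
- Section 4c, Blinding: "where the primary objectives are to assess tolerability and dose, blinding is not appropriate", and "There is no placebo or non-treatment group that would require blinding".
- Section 7b: "Port-wine score" is one of seven secondary outcome variables.
- Section 8d: "Photographs will be stored in a digital, locked research database". Where a participant chooses destruction, it follows analysis and publication.
- Section 6a cites effects of cannabidiol on abnormal angiogenesis and expects such effects to help in Sturge-Weber syndrome. Section 3 includes the facial vascular birthmark in the description of that syndrome.

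**The concern.** Coverage, thickness and darkness of a birthmark are matters of judgement. A scorer who knows which image is baseline and which is on drug, and who has reason to expect improvement, may score the later image a little better without intending to. With no comparison group, nothing subtracts that shift from the mean change. The argument in section 4c concerns concealment of treatment. Concealing the order of photographs needs no control arm and leaves the open-label design as it is. At stake is whether a reported change in port-wine score can be read as a change in the birthmark. Section 7c intends promising results to feed the sample size of follow-up studies, so a biased change score could be carried forward if this outcome were used for that purpose.

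**Working it through.** **1. No figure to reproduce.** The plan gives no test, significance level, SD or reliability for the port-wine score, and section 7c states that no sample size calculation was done. The core of the point is therefore a comparison of passages.

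**2. Passages side by side.**
- Section 4a fixes how photographs are taken and what is scored. It leaves open who scores, when, and with what knowledge of the visit.
- The form-completion rule, if it covers this score, puts scoring at the visit, where the visit number is known. It is a general rule and does not mention photographs.
- Section 4c gives two reasons against blinding: the objectives are tolerability and dose, and there is no comparator. Neither bears on whether a photograph reader should know the visit.
- Section 6a supplies a direction of expectation.
- Section 8d keeps the images until analysis is finished, so later scoring in a random order is possible.

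**3. How the bias enters.** For one subject, observed change = true drug effect + natural change + reader shift + error. The single-arm mean estimates the sum of the first three terms. Masked random-order reading acts only on the third.

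**4. Illustration (all inputs assumed except the ceiling on n).** Suppose no true or natural change, a reader shift of d SDs of the change score, and a two-sided 5% paired t-test. The test statistic then follows a noncentral t distribution with n − 1 degrees of freedom and noncentrality d√n. The rejection rate is P(T > t*) + P(T < −t*), where t* is the 97.5% point of the central t.

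The upper limit n = 10 is the enrolment in section 5. Only subjects with a facial birthmark give a change score, and their number is not stated, so n = 7 and n = 5 are shown as well.

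| n | t* | d = 0.3: d√n, rate | d = 0.5: d√n, rate | d = 0.8: d√n, rate |
|---|---|---|---|---|
| 10 | 2.262 | 0.949, 14% | 1.581, 29% | 2.530, 62% |
| 7 | 2.447 | 0.794, 10% | 1.323, 20% | 2.117, 43% |
| 5 | 2.776 | 0.671, 8% | 1.118, 14% | 1.789, 28% |

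With d = 0 every rate is 5%. The bias in the mean change is d SDs whatever the test or n; only the rejection rate depends on them.

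**The case against.** **Silence is not a statement.** A reader might infer that the photographs are scored by someone who knows the visit, or that the investigators decided against masked reading. The documents support neither. They do not describe the scoring arrangement, section 4c does not mention outcome reading, and the Study Visit Table was not available. What stands is that no masking is specified.

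**The reader is unknown.** It is tempting to assume a single scorer, perhaps the clinician who assigns the neuroscores. The plan does not say so. If the scorer also treats the subjects, memory of the visits may partly defeat the coding.

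**Masking cannot remove the bias.** Subjects may be as young as 1 month, and treatment through the Optimization Phase runs about 42 weeks (14 + 28). Growth alone can reveal the order of images. Thickness is hard to judge from a photograph and may be scored in person. Natural change over time remains in any single-arm comparison. All of this stands: the remedy reduces expectation bias and does no more.

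**The rejection rates do not describe a planned analysis.** No t-test is planned, so there is no planned 5% error rate to inflate, and n = 10 holds only if every subject has a facial birthmark. This stands too, and the table is illustration only.

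**The outcome is peripheral.** It does not enter the treatment-failure and removal criteria in section 4f or the stopping rule in section 7c. That limits the weight of the point. It does not answer it, because the photographs are taken for research and the score is a listed outcome.

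**Conclusion.** The point holds in limited form. The plan specifies no masking of visit order for a judgement-based secondary outcome, and its reason for not blinding does not apply to reading stored images. The design therefore leaves room for an expectation bias that could be reduced cheaply.

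Its actual size cannot be derived from the documents. Under the assumed shifts of 0.3 to 0.8 SD, rejection with no true change would range from 14% to 62% at the ceiling of 10 subjects and from 8% to 28% with 5. A reader might take these as the study's false-positive rates. They are not, since they rest on an unplanned test, assumed shifts and an unknown number of contributing subjects.

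Seizure frequency, tolerability and dose finding are unaffected. The change is worth considering and is not a condition for the study's main conclusions.

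**What to change.** Amend the photograph item in section 4a to state that:

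- one existing study-team member scores all of a subject's photographs in batches, in random order, under coded file names with visit and date removed;
- these scores are the ones used for the port-wine outcome in section 7b;
- any thickness component scored in person is unmasked and is reported as such.

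Add a sentence to section 4c saying that the open-label design does not prevent masked reading of photographs. Report the number of subjects with a facial birthmark who contribute to the change score, and note that growth in young children may reveal image order.

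The cost is some file coding by existing staff and later availability of the scores. No extra reader, visit or procedure is needed. That the cost is low is inferred from the digital storage and the small enrolment; the plan does not state it. Because the images are kept until analysis and publication, the reading can also be done after collection has finished.
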